8.2 Planned statistical analysis

8.2.1 Statistical analysis plan

A statistical analysis plan (SAP) describing in detail all statistical analyses performed will be elaborated. An intermediate progress report will be made after 1 year of inclusion to evaluate the robustness of the study with regards to estimated initial inclusion rates, expected age categories, risk predictions, and compliance to screening recommendations, on the overall population and at the country level to recommend potential changes to the protocol and/or study management. Indeed if the age and risk structure of the population appeared significantly different from those expected, with potential important influence on the study's power or ability to conclude, amendments may be proposed by the Clinical Trial Steering Committee, upon advice of the Ethics and data Monitoring Committee.

This progress report will be updated after 2 years of inclusion and during the follow-up period after the last woman randomization.

Beside this, the spread of SNPs chosen and harmonious population repartition will be verified after 5,000 women are included.

All the analyses for the progress reports will be conducted blinded from the efficacy outcomes of the study (breast cancer incidence). Once all the participants have been followed for 4 years, the cleaned database will be locked and a final statistical report prepared.

The primary analysis will compare the cumulative hazard functions of cancers of stage 2 + between the two randomized groups of women using a logrank test. The rate of cancers of stage 2 + cancers for each arm will be estimated as the number of cancers of stage 2 + detected either clinically or by screening out of the total person-years of follow-up.

The primary non-inferiority analysis will be performed on the per-protocol (PP) population, which will include all randomized and eligible women in the arm they were randomized to, who complied with their screening recommendation in terms of number of mammograms. The analyses will be repeated in the Intention-To-Treat (ITT) population for sensitivity. An additional sensitivity analysis, we will be performed using causal inference methods to estimate the average effect of the risk-based screening versus standard screening on stage 2 incidence as if all participants will have complied with the protocol.

If non-inferiority of the risk-stratified screening arm relative to the control arm is concluded for the primary endpoint, then superiority of the risk screening arm will be tested against the standard arm (closed testing procedure). The inferential superiority analysis will be performed in the ITT population, with the PP and causal inference analysis for sensitivity. We estimate that for the superiority analysis we will have at least 80% power to detect a 30% relative decrease in the risk-based arm.

In another additional sensitivity analysis, we will exclude all prevalent cases (cancer detected 2 months after the first mammography) from the analysis and focus on women with no cancer at study entry in order to re-evaluate the benefit of risk-adapted screening thereafter.

Standard statistical methods as Kaplan-Meier analyses, Cox proportional cause-specific hazards regression will be used to compare the time-to-event variables between the 2 study arms and estimate hazard ratios adjusted for the stratification factors at a one-sided 0.025 significance level.

A multivariable model will also be constructed using relevant key risk factors of breast cancer on the different time-to-event endpoints. A competing risk cumulative incidence approach will also be applied.

The overall excess overdiagnosis with risk-stratified screening compared to standard screening will be estimated from the study. Different lead time models will be applied to obtain a range of mode-based estimates of overdiagnosis; a microsimulation model will be calibrated to the study population for overdiagnosis estimates, and cost and cost-effectiveness evaluations.

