8.1 Statistical hypothesis and sample size determination

Randomization

Women who have signed the informed consent will be assigned a unique participant identifier and will be randomized 1:1 to either standard screening or the risk-based screening strategy. Randomization will be performed through an automated real-time online system (permutation blocks).

Stratification

Randomization will be stratified by country, age (women aged <50 vs ≥ 50), and prior mammogram (yes or no). This will ensure to balance screening modalities, global population risks, and the rate of prevalent breast cancers at entry.

Required number of women to be included

The incidence rate of stage 2 + breast cancer in the MyPeBS standard arm is expected to be around 120 cases/100,000/year. This number is derived from what is observed in the screened populations of European countries and including women aged 40 to 50 years for whom the incidence rate is lower:

- Incidence in women aged 50-74 years old is 140 cases/100,000 women/year on average in screened populations taking into account interval cancers and cancers not detected in women who are not screened
- We expect to include 25% of women aged between 40-49 years old
- Incidence in women aged 40-49 years old is half than older women
- Expected incidence of stage 2+ breast cancers for 100,000 women followed up for 1-year in the standard arm of MyPeBS is therefore: $(140 \times 0.75) + (0.25 \times 0.5 \times 140) = 105 + 17.5 = 122$. A slightly conservative estimate is therefore 120.

We anticipate a drop-out rate lower than 5% in both arms, and non-compliance rates of 10% in the risk-based screening arm and of 30% in the standard arm. These women will not be included in the per-protocol analysis due to non-compliance, in the 4-year period after inclusion.

The primary hypothesis is that the risk-based screening arm will be non-inferior to the standard screening arm in terms of cumulative hazard rate in the per-protocol population. The cumulative hazard functions of cancers of stage 2 + will be compared between the 2 study arms.

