Further assumptions are a non-inferiority margin of a 25% relative increase in the risk-based arm (null hypothesis $H_0: \lambda_e/\lambda_c \geq 1.25$ with t and c standing for experimental and standard arm, respectively; it corresponds to an absolute increase in the cumulative hazard rate of stage 2 cancer or higher after 4 years up to 120/100000 stage 2 cancers the risk-based arm under H_0), 80% power, 2.5% significance level, 1-sided test. If we assume that under the alternative hypothesis a 10% relative improvement can be expected by the experimental risk-based-stratified screening arm (i.e. $\lambda_e/\lambda_c = 0.9$) due to our anticipated increase in the average numbers of mammograms in the experimental arm, a total of 298 stage 2 breast cancers are required for the non-inferiority assessment using a logrank test. We assume a total of 85,000 participants, 42,500 in each arm, to be included over 2.5 years.

For the primary and key secondary endpoint analysis, each subject will be followed for four years, to be able to compare cycles of mammograms between the 2 screening arms. Later updates of the trial analyses will be performed using longer follow-up.

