8.3.2 Definition of intent to treat population for the main secondary endpoint analysis

Intent to treat population comprises all women randomized to either study arm and evaluable for the main secondary endpoint analysis, whatever was their compliance with the screening schedule they were assigned to.

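### Non-inferiority is decided in the per-protocol set alone, with 30% versus 10% planned exclusion and no requirement that ITT agree

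*Protocol*

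**What the plan says.** Section 8.1 places the primary hypothesis in the per-protocol population. It assumes a "non-inferiority margin of a 25% relative increase in the risk-based arm", "80% power, 2.5% significance level, 1-sided test", and that "a 10% relative improvement can be expected by the experimental risk-based-stratified screening arm". On that basis "a total of 298 stage 2 breast cancers are required for the non-inferiority assessment using a logrank test". It anticipates "non-compliance rates of 10% in the risk-based screening arm and of 30% in the standard arm" and states that these women leave the per-protocol analysis.

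Section 8.3.1 defines compliance by the number of mammograms over the 4 years after randomization. The limits differ by arm, age, country and risk level. For example, most standard-arm women aged 50-70 need at least one mammogram and high-risk women in the risk-based arm need at least two.

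The primary test in section 8.2.1 compares the "cumulative hazard functions of cancers of stage 2 + between the two randomized groups of women using a logrank test". For the other analysis set, "The analyses will be repeated in the Intention-To-Treat (ITT) population for sensitivity". A causal-inference analysis, estimating the effect under full compliance, is a further sensitivity analysis. The same section also plans Cox HRs adjusted for the stratification factors at the one-sided 0.025 level. Superiority is tested only after non-inferiority, with ITT as the inferential set.

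Section 8.2.2, on decision rules, states only when the final analysis takes place. Section 8.3.2 defines ITT as "all women randomized to either study arm and evaluable for the main secondary endpoint analysis", whatever their compliance.

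**The concern.** PP membership depends on behaviour after randomization, and the plan expects three times as much exclusion in one arm as in the other. What remains is no longer a randomized comparison. If excluded women differ from retained women in their rate of stage 2+ cancer, the PP HR mixes the effect of the strategy with the effect of who was kept.

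The protocol's own background (section 1.1.2) shows that the analysis set matters in screening trials: about a 20% mortality reduction in intention-to-treat populations against 30-40% in per-protocol ones.

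The trial reduces screening for part of its population, and section 1.1.14 explains the non-inferiority objective by the wish to avoid harm. A false non-inferiority claim is therefore the error that matters most. As written, a PP success stands even if the ITT analysis fails to exclude a 25% increase.

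**Working it through.** **Inputs (section 8.1).** Margin 1.25; planned HR 0.90; one-sided alpha 0.025; power 80%; 42,500 women per arm; 4 years; 120 events per 100,000 per year in the standard arm; drop-out below 5%; PP retention 70% standard and 90% risk-based.

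**1. Required events.** The ratio to detect is 0.90/1.25 = 0.72, and (1.960 + 0.842)² = 7.849.
- Schoenfeld, 1:1: 4 × 7.849 / (ln 0.72)² = 291.
- Freedman: 7.849 × (1.72/0.28)² = 297.
- Schoenfeld at the PP allocation 0.9:0.7 (share 0.5625): 7.849 / (0.5625 × 0.4375 × (ln 0.72)²) = 296.

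All are within 3% of the stated 298, so the event target is sound.

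**2. Expected events.** Full follow-up in the standard arm gives 42,500 × 4 × 0.0012 = 204.
- PP, 5% drop-out: 204 × 0.95 × 0.7 = 136 and 204 × 0.95 × 0.9 × 0.9 = 157, total 293. With no drop-out: 143 + 165 = 308.
- ITT at HR 0.90: 204 × 0.95 × 1.9 = 368; with no drop-out, 388.

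The 298 is met in the PP set after the 30%/10% exclusion, so the unequal exclusion is part of the design. With 5% drop-out the PP set has about 28,260 standard-arm and 36,340 risk-based women.

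**3. Effect of selection.** Let k be the event rate of excluded women relative to retained women, the same in both arms. The documents give no value, so k is an assumption. Each arm's ITT rate equals its retained rate times (0.7 + 0.3k) or (0.9 + 0.1k), so

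PP HR = ITT HR × (0.7 + 0.3k) / (0.9 + 0.1k).

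Set the true ITT HR at the margin, 1.25, with 5% drop-out. With D the PP events per arm and SE = √(1/D_std + 1/D_risk), the chance of a PP claim is Φ(ln(1.25/PP HR)/SE − 1.96).

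| k | PP HR | PP events (standard, risk-based) | Chance of PP claim |
|---|---|---|---|
| 0.5 | 1.12 | 160, 229 | 19% |
| 0.75 | 1.19 | 147, 224 | 7% |
| 1 | 1.25 | 136, 218 | 2.5% |
| 1.5 | 1.37 | 118, 208 | 0.3% |

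For k = 0.5: 1.25 × 0.85/0.95 = 1.12, SE = 0.103, and Φ(0.111/0.103 − 1.96) = Φ(−0.88) = 0.19.

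**4. Power if both sets must succeed.** The two test statistics are treated as bivariate normal. The PP events are a subset of the ITT events, so the correlation is about √(293/368) = 0.89. With 5% drop-out, the mean z is −ln(0.72) × √(293/4) = 2.81 for PP and −ln(ITT HR/1.25) × √(events/4) for ITT. PP HR is held at 0.90; ITT HRs above 0.90 are assumed dilution.

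| ITT HR | ITT events | ITT power | Joint power |
|---|---|---|---|
| 0.90 | 368 | 88% | 78-79% |
| 0.95 | 378 | 76% | 72% |
| 1.00 | 388 | 59% | 58% |

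PP alone has 80%. With no drop-out and an ITT HR of 0.90, joint power is about 81%.

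**The case against.** The strongest defence is that PP as the primary non-inferiority set is deliberate, prespecified and powered. Non-compliance can pull ITT towards no difference, so ITT alone may also be too lenient for non-inferiority. The plan also runs ITT and a causal-inference analysis aimed at this selection problem, and compliance is reviewed in progress reports that may lead to amendments. All of this stands. It argues against replacing PP by ITT. It does not supply a rule for what happens when the analyses disagree.

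Four stronger readings are tempting, and the documents support none of them.
- **The primary test is unstratified.** The protocol says only that it is a logrank test. It does not say whether it is stratified, it plans a stratification-adjusted Cox HR in the same section, and a SAP not shown here may settle the point.
- **A wrong PP result does harm by opening the superiority test.** Superiority is inferential in ITT. If the ITT upper limit exceeds 1.25 it cannot be below 1, so that test fails.
- **The bias favours non-inferiority.** The last row of the selection table runs the other way. Section 8.3.1 gives no rule for a woman whose cancer is found before she reaches her mammogram minimum, but that rule may sit in the SAP and its net effect cannot be derived from the protocol.
- **ITT is cut down to a selected subset.** The word evaluable is undefined, but the definition keeps women whatever their compliance.

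**Conclusion.** The concern holds as a missing decision rule. Non-inferiority rests on PP alone under unequal, post-randomization exclusion, and neither ITT nor the causal-inference analysis can block the claim. With a true ITT HR at the margin, the chance of a claim ranges from 0.3% to 19% for excluded-to-retained rate ratios from 1.5 down to 0.5, instead of the nominal 2.5%. That range rests on assumed rate ratios, equal in both arms, and on the protocol's 30%/10% exclusion. It shows sensitivity, not a predicted bias. The event target itself is not in question.

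**What to change.** In sections 8.2.1 and 8.2.2, state that non-inferiority is concluded only if the upper limit of the one-sided 97.5% confidence interval of the HR is below 1.25 in both PP and ITT. In section 8.3.2, define ITT for this purpose as all randomized women, censored at last contact. Name the HR adjusted for country, age group and prior mammogram, which section 8.2.1 already plans, as the one used for the decision. The adjustment removes imbalance between strata created by exclusion; it does not remove selection within strata, which is why ITT must also succeed.

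The change is one of wording and needs no additional women at the planned HR. The cost in power should be stated as a range. With 5% drop-out, it is 1 to 2 points if the ITT HR is also 0.90 (78-79% against 80%), about 8 points if non-compliance dilutes it to 0.95, and about 22 points at 1.00. The sponsor should state the dilution it expects and fix the rule before outcome data are seen.

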8.2.2 Final analyses decision rules

Final analyses will be conducted once all participants accrued and who have remained on study have reached 4 years from randomization.

8.2.3 Accrual rates and accrual duration

Accrual duration is 2.5 years (1st patient in until last patient in)

Accrual will be competitive throughout the trial

Accrual rates will be carefully monitored and reported

8.3 Study populations to be analysed

8.3.1 Definition of per-protocol population for the primary endpoint analysis

The per-protocol (PP) population will include all randomized and eligible women in the arm they were randomized to who complied with their screening recommendation.

Per-protocol definition of compliance (the study entry mammogram, if any, will not be considered) will be used for the primary analysis of the trial and is described below, according to randomization arm:

Per-protocol definition for standard arm:

Standard arm				
(either no mammogram or mammogram(s)/1-2-3 years according to age and country – will be defined individually at entry)				
Population	40-49 (France, Belgium, UK and Israel) 40-44 (All women of Italy) 45-49 (for some women depending the region of Italy)	50-70 (UK)	50-70 (France, Belgium, Italy and Israel)	45-49 (Some region of Italy)
Planned images	No mammogram	Mammogram every 3 years	Mammogram every 2 years	Mammogram every year
Per-protocol definition	≤ 1 mammogram over 4 years	≥ 1 mammogram over 4 years AND < 4 mammograms over 4 years (excluding diagnostic mammograms)	≥ 1 mammograms over 4 years AND < 4 mammograms over 4 years (excluding diagnostic mammograms)	≥ 2 mammograms over 4 years

Per-protocol definition for risk-based arm:

Risk-based arm				
	Low risk	Average risk	High risk	Very high risk
Planned images	Mammogram every 4 years +/- US if dense breast	Mammogram every 2 years +/- US if dense breast	Mammogram every year +/- US if dense breast	Mammogram + MRI every year for women < 60
Per-protocol definition (outside of baseline and end of study mammo)	≤ 1 mammograms over the 4 years	≥ 1 mammograms over 4 years AND < 4 mammograms over 4 years (excluding diagnostic mammograms)	≥ 2 mammogram over 4 years	≥ 3 mammograms over 4 years ≥ 3 MRIs over 4 years

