Women randomized to the risk-based arm will be asked to provide a saliva sample (see below). Their breast density will be evaluated. They will be scheduled for a second visit, during which they will be communicated their risk estimation and their personalized, risk-based, screening schedule/plan for the next 4 years.

TRIAL CONDUCT IN THE STANDARD ARM

In the standard arm of MyPeBS, women will be screened for breast cancer according to the current national guidelines and procedures: with a mammogram and/or tomosynthesis (TS) every two or three years starting at age 40-50 years, up to age 69-74 years according to countries, with or without ultrasound (US) according to breast mammographic density and ongoing guidelines. The current national/regional guidelines in use in the including center may be subjected to changes during the study. Guidelines and procedures in the standard arm will be updated accordingly. Current guidelines by country and age, applicable to the standard arm are described in Table 2.

BREAST CANCER RISK REDUCTION MEASURES

Participants in the standard arm will be informed of potential risk-reducing strategies. They will be provided written and on-line information material and encouraged on follow these predefined measures.

Participating women will receive standardized self-awareness recommendations, although they will remain free to comply with them or not.

STUDY CONDUCT IN THE RISK-BASED ARM

Women in the risk-based arm will provide a saliva sample during visit 0 (baseline). This sample will be sent out for centralized genotyping.

[figure not shown]
During a second dedicated visit (8-12 weeks after the initial visit) risk-estimation will be delivered and explained to women. This is the moment when they will be proposed their personal screening program. This visit may be physical or by telephone interview depending on the countries.

ESTIMATION OF 5-YEAR BREAST CANCER RISK FOR WOMEN RANDOMIZED IN THE RISK-BASED ARM / RISK STRATIFICATION

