Israel: http://en.cancer.org.il/template_e/default.aspx?PagelId=7749

Belgium: <https://www.ccref.org/old/pdf/MB25112000.pdf>; <https://www.ccref.org/old/pdf/MB10082001.pdf>; and Royal decree establishing the necessary standards for the accreditation of specialist breast cancer centres in Belgium – January 1st 2008.

France: http://www.has-sante.fr/portail/jcms/c_1741170/fr/depistage-du-cancer-du-sein-en-france-identification-des-femmes-a-haut-risque-et-modalites-de-depistage, <http://www.e-cancer.fr/Professionnels-de-sante/Depistage-et-detection-precoce/Depistage-du-cancer-du-sein/Orienter-vos-patientes>)

The current national/European guidelines in use may vary during the trial, at a national or European level. Guidelines and procedures in the standard arm will be updated accordingly and timely.

All participating countries have specific guidelines for:

- **High-risk women** defined as having had a previous breast cancer or high-risk situations including radiation therapy for Hodgkin's disease or atypical hyperplasia. These women will not be eligible for MyPeBS
- **Very high-risk women** defined as having a germline mutation of either BRCA1 or BRCA2 genes or an equivalent situation. These women will not be included in MyPeBS

1.1.3 “4P medicine” and application to breast cancer screening

Personalized cancer prevention approach (meaning personalized risk assessment together with specific individual screening and primary prevention) is a major public health challenge. However, this approach needs individual risk identification, adequate perception and awareness leading to changes in behaviors towards cancer prevention. It also requires reaching the adequate population and avoiding disparities in health care access. This is included in the so-called P4 medicine (Predictive, Personalized, Preventive, and Participatory) (Hood 2011).

Risk based prevention is highly efficient in other public health models

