3.1.3 Randomization

Women who have signed the informed consent and fulfill all eligibility criteria will be randomized directly online by the investigator (see 3.4.2)

The results of the randomization will be immediately provided to both the investigator and the woman.

- Women randomized to the standard arm will immediately receive their personal "standard" screening schedule for the next 4 years. No other study visit with the investigator is formally planned.
- Women randomized to the risk-based arm will be asked to provide a saliva sample (see below). Their breast density will be evaluated. They will be scheduled for a second visit (physical or by telephone interview according to national/local regulations), during which they will be communicated their risk estimation and their personalized, risk-based, screening schedule/plan for the next 4 years.

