5. INTERVENTIONS

5.1 Trial conduct if the standard arm

In the standard arm of MyPeBS, women are screened for breast cancer according to the current national guidelines and procedures:

- Bi-yearly or tri-yearly mammogram and/or tomosynthesis starting at age 40-50, up to age 69-70 according to countries, with or without Ultrasound (US) according to breast mammographic density and ongoing guidelines.
- The current national/regional guidelines in use in the including center may be subjected to change during the trial. Guidelines and procedures in the standard arm will be updated accordingly. Current per country and per age guidelines applicable to standard arm are described in table 2.

Breast cancer risk reduction measures:

Participants in the standard arm will be informed of potential risk-reducing strategies. They will be provided written and on-line information material and encouraged to follow these predefined measures.

Participating women will receive standardized self-awareness recommendations, although they will remain free to comply with them or not.

BREAST CANCER SCREENING SCHEME IN THE **STANDARD** ARM

Standard arm (either no mammogram or mammogram(s)/1-2-3 years according to age and country – will be defined individually at entry)				
Population	40-49 (France, Belgium, UK and Israel) 40-44 (All women of Italy) 45-49 (for some women depending the region of Italy)	50-70 (UK)	50-70 (France, Belgium, Italy and Israel)	45-49 (Some regions of Italy)
Planned images	No mammogram	Mammogram* every 3 years	Mammogram* every 2 years	Mammogram* every year

* Or Tomosynthesis + synthetic 2D if applicable in the country/center

As stated, all participating countries have specific guidelines for:

- High-risk women defined as having had a previous breast cancer or high-risk situations including radiation therapy for Hodgkin's disease or atypical hyperplasia. These women will not be eligible for MyPeBS
- Very high-risk women defined as having a germline mutation of either BRCA1 or BRCA2 genes or an equivalent situation. The women already identified as such will not be included in MyPeBS

A summary of ongoing guidelines in the participating countries at the time of the final design the present protocol is shown below:

Country	Region	Age eligibility in OS	Mammographic screening frequency	2 nd reading	Ultrasound policy	Tomosynthesis policy	Other
Belgium	Brussels	50-69	2 years	Yes	Not included in program	Outside OS	No CBE
	Leuven					Within OS	

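### Read literally, the per-protocol table in 8.3.1 drops some controls who reach screening age during follow-up and attend both rounds due, and keeps those who attend none

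*Protocol*

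**What the plan says.** Section 8.2.1 makes the per-protocol analysis primary for non-inferiority, with intention-to-treat and causal-inference analyses as sensitivity analyses. Section 8.3.1 admits women "who complied with their screening recommendation" and says that the definition which follows will be used for the primary analysis.

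The standard-arm table then sets the limits by column, and the applicable regime "will be defined individually at entry":

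- Ages 40-49 in France, Belgium, the UK and Israel, all Italian women aged 40-44, and some aged 45-49: none planned; compliant if "≤ 1 mammogram over 4 years".
- Ages 50-70, biennial or triennial: compliant with 1 to 3 mammograms.
- Ages 45-49 in some Italian regions, yearly: compliant if "≥ 2 mammograms over 4 years".

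Section 3.1.3 gives each control a personal "screening schedule for the next 4 years". The guideline summary in 5.1 shows programmes starting at 50, every two years in Belgium, France, Israel and Italy and every three in the UK, with yearly screening from 45 in some Italian regions. Section 3.1.4 gives the exit mammogram only to those controls whose age meant that they had no screening mammogram in the four years. Guidelines may also change during the study, and "Guidelines and procedures in the standard arm will be updated accordingly" (5.1).

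**The concern.** Some women under screening age at entry will come into their national programme during the four years, with no guideline change at all. The limit of one covers a woman with a single round due, but not one with two. A French control aged 49 who attends at 50 and 52 has done what her programme asked, yet she has two mammograms against a limit of one. Her neighbour who ignores both invitations passes.

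The protocol does not say whether the column follows age at entry or attained age. Membership of the primary analysis set therefore depends on a reading chosen after randomization in an open-label trial. On the literal reading the rule selects against attenders. It does so in the standard arm only, because the risk-based table classifies by risk level, not age.

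**Working it through.** **Plan's own figure.** The margin is 1.25 and the assumed hazard ratio 0.9, so the ratio is 0.72 (one-sided 2.5%, 80% power). The Schoenfeld formula, (1.960 + 0.842)² / (0.25 × ln(0.72)²), gives 291 events. Freedman's, (1.960 + 0.842)² × (1.72/0.28)², gives 297. Section 8.1 states 298, so it reproduces to within 3%.

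**Who can have two rounds due** (first round at 50):

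- Biennial: the second round is at 52, so entry age 48 or 49.
- UK, triennial: the second round is at 53, so entry age 49.
- Italian regions yearly from 45: two rounds from entry age 42, three from 43, four from 44.

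**How many.** Half of the synopsis country targets gives standard-arm numbers of 10,000 (France), 5,000 (Belgium), 15,000 (Italy), 7,500 (Israel) and 5,000 (UK). Section 8.1 expects 25% to be aged 40-49: 2,500 + 1,250 + 3,750 + 1,875 + 1,250 = 10,625. An even spread over ten single years is assumed.

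- Ages 48-49 (2/10): 500 + 250 + 750 + 375 = 1,875, or 4.4% of 42,500.
- First invitation a year late, so age 49 only (1/10): 250 + 125 + 375 + 187.5 ≈ 938, or 2.2%.
- UK, age 49, prompt invitation: up to 125 more.
- Italy is counted at 2/10. If every Italian region screened yearly from 45, ages 42-44 would make it 3/10, or 375 more. Only some regions do.

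**How many attend both.** Take 70% attendance per round (assumed). Both rounds are attended by 0.7² = 49% if rounds are independent and by 70% if the same women always attend. This gives 938 × 0.49 ≈ 460 to 1,875 × 0.70 ≈ 1,310 women.

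**Events.** The protocol's rate for ages 40-49 is half of 140, or 70 per 100,000 per year, which is 0.0028 over four years. Events removed: 460 × 0.0028 ≈ 1.3 to 1,310 × 0.0028 ≈ 3.7. At the 50-plus rate of 140 the upper figure is about 7.3.

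**Power.** Events per arm before exclusions: 42,500 × 4 × 0.0012 = 204. Per-protocol: 204 × 0.95 × 0.70 = 135.7 (standard) and 204 × 0.95 × 0.90 × 0.9 = 157.0 (risk-based). Power = Φ(ln(1.25/0.9) / √(1/d₁ + 1/d₂) − 1.96).

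| Standard-arm events removed | Power |
|---|---|
| 0 | 80.0% |
| 1.3 | 79.8% |
| 3.7 | 79.4% |
| 7.35 | 78.8% |

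This subtracts the events on top of the planned 30% non-compliance, which is 12,750 women. The 460 to 1,310 are 4% to 10% of that number. If they are already inside it, the loss against plan is zero.

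**Direction.** The standard per-protocol set is 42,500 × 0.665 ≈ 28,262 women at 122.5 per 100,000 (the unrounded figure in 8.1). Removing 1,310 women at a rate of 70 gives (34.62 − 0.92) / 26,952 = 125.1, a rise of 2.1% that would favour non-inferiority. Removing them at 140 gives (34.62 − 1.83) / 26,952 = 121.6, a fall of 0.7%. The sign depends on the rate in these women, who are at the upper edge of the 40-49 band.

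**The case against.** The best reply is that the table carries out the lead sentence of 8.3.1 and is not a rival to it. The regime is set individually, each control has a personal four-year schedule, and 3.1.4 already takes age during follow-up into account. On that view a woman of 49 with two rounds on her schedule was never in the no-mammogram column. This is a sensible reading and may well be what was meant, so it would go too far to say that the protocol contradicts itself outright. But it is not written, and she does fall under a column headed 40-49.

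It can also be said that age-band handling belongs in the SAP, which is not at hand. The SAP may settle it. However, 8.3.1 itself fixes the numerical rule for the primary analysis, and the rule as printed misclassifies these women.

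Three stronger inferences are not supported:

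- **Guideline changes will empty the control set.** The synopsis says only that "The current national/regional guidelines in use in the including center may be subjected to changes during the study". Nothing says that any region will start screening below 50, and 8.2.1 provides for progress reports and amendments.
- **The rule biases towards non-inferiority.** The sign is not established. Section 1.2.1 reports a relative risk for higher-stage cancer of 0.98 at 39-49 but 0.62 at 50 and over. The Cox estimates in 8.2.1, adjusted for stratification factors, would absorb much of a shift due only to age mix.
- **Older controls are caught too.** A switch between biennial and triennial screening at 50-70 changes nothing, because both columns accept 1 to 3.

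**Conclusion.** The point stands as a minor one. Read literally, 8.3.1 excludes from the primary per-protocol set a small group of controls who did what was recommended and retains those who attended nothing, in one arm only. About 940 to 1,875 women have two rounds due and about 460 to 1,310 attend both. At most about 1 percentage point of power is lost, and perhaps none. No effect on the trial's conclusion is shown, and the intention-to-treat and causal-inference analyses give further protection. The counts rest on an even age spread within 40-49, 70% attendance per round, first invitations between prompt and one year late, and the target country mix. The reason to act is that membership of the primary set should not depend on an unwritten choice.

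**What to change.** Add to 8.3.1 that a control below screening age at entry who has two or more programme rounds due during her four years is judged by the column for the schedule then due:

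- 1 to 3 mammograms under biennial or triennial screening, and likewise where exactly two yearly rounds are due;
- at least 2 where three or more yearly rounds are due.

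Keep the limit of one for women with none or one round due. Apply the same rule if a regional guideline change makes rounds due, and keep a dated list of such changes.

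The cost is one sentence and a slightly more complex compliance algorithm. Women with two or more rounds due who attend too few would now leave the set: none attended, or fewer than two where three or more yearly rounds are due. With two biennial rounds due and 70% attendance that is up to 1,875 × 0.30 ≈ 560 women. The gain is therefore correct classification more than a larger set.
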